Given the risk for fluid and electrolyte imbalances, close monitoring will be provided for the DPR group by using more frequent clinical and laboratory assessments in addition to standard NICU monitoring. Vital signs and strict intake and output will be monitored every 6 hrs for 48 hours after maximum dialysate infusion volume (100 mL) is reached, then every 12 hrs (\pm 30 minutes). Sodium, potassium, blood glucose and lactate levels will be monitored every 6 hours (\pm 30 minutes) via heelstick, central/arterial line or venipuncture per NICU standard practice for 24 hours after the maximum dialysate infusion volume is reached, then every 12 hrs (\pm 30 minutes) through Post-Closure Day 1.

Title: Direct Peritoneal Resuscitation in Gastroschisis

PI: [name]

Sponsor: UAMS

Subject will also be monitored for the following potential adverse events:

1. Hypokalemia: If the potassium falls to <3.0, additional potassium will be added to the IV fluid at the discretion of the treating and study physicians.
2. Lactic acidosis: Lactate levels will be monitored with laboratory checks at least every 12 hours during the treatment phase. Continued monitoring of lactic acidosis will include laboratory checks, fluid replacement, and stopping infusion of the dialysate fluid.
3. Hyperglycemia: During the first day (24 hrs) of treatment, blood glucose will be obtained within 1 hour prior to infusion and 1 hour (\pm 15 minutes) post-infusion in addition to routine daily assessments. The neonatologists will change IVFs to contain less dextrose as needed.
4. Hypovolemia: This will be treated with fluid replacement. Blood pressure monitoring and urine output assessment will guide management for amount of fluid replacement needed.
5. Peritonitis: This will be evaluated daily by examination of the effluent dialysate for any cloudiness. Cloudy fluid will be sent to the laboratory for cell count, gram stain, and culture. If the cell count is elevated, the subject will receive antibiotics as indicated. Subjects with confirmed peritonitis will be withdrawn from the study.
6. Definite (culture positive) sepsis: Neonates with active clinical sepsis will be excluded from the study by the hemodynamic parameter exclusion criteria (hypotension, hyper/hypoglycemia, lactic acidosis, etc.). During the dialysate infusion period, subjects who develop definite (culture positive) sepsis will be withdrawn from the study.
7. Acute Kidney Injury (AKI): AKI will be staged using the “Neonatal AKI KDIGO Classification” Table below (Selewski *et al* [22]). Subjects who develop AKI > Stage 2 will be withdrawn from the study.

TABLE 1 Neonatal AKI KDIGO Classification

Stage	SCr	Urine Output
0	No change in SCr or rise <0.3 mg/dL	≥ 0.5 mL/kg/h
1	SCr rise ≥ 0.3 mg/dL within 48 h or SCr rise $\geq 1.5\text{--}1.9 \times$ reference SCr ^a within 7 d	<0.5 mL/kg/h for 6 to 12 h
2	SCr rise $\geq 2.0\text{--}2.9 \times$ reference SCr ^a	<0.5 mL/kg/h for ≥ 12 h
3	SCr rise $\geq 3 \times$ reference SCr ^a or SCr ≥ 2.5 mg/dL ^b or Receipt of dialysis	<0.3 mL/kg/h for ≥ 24 h or anuria for ≥ 12 h

Differences between the proposed neonatal AKI definition and KDIGO include the following:

^a Reference SCr will be defined as the lowest previous SCr value.

^b SCr value of 2.5 mg/dL represents <10 mL/min/1.73m².

Individual Subject Discontinuation

If a subject develops any of the individual subject discontinuation criteria below, the study drug will be immediately discontinued:

- Positive blood culture
- Documented peritonitis
- Lactic acid > 5 mmol/L
- pH < 7.1
- Sodium < 125 mEq/L or > 150 mEq/L
- Potassium < 2.5 mEq/L
- Continued hyperglycemia > 250 for more than 12 hours
- Definite (culture positive) sepsis
- Stage 3 AKI [22]

Title: Direct Peritoneal Resuscitation in Gastroschisis

PI: [name]

Sponsor: UAMS

Subjects who develop any of the individual subject discontinuation criteria will be evaluated and monitored until resolution of the adverse events and laboratory values have returned to baseline. These subjects will no longer receive DPR, but will continue with assessments per the schedule of procedures and assessments.

Study Discontinuation

The study will be stopped if more than 3 subjects in the DPR group develop any one of the individual subject discontinuation criterion above.

Adverse Events

For purposes of this study, the following will be considered adverse events of special interest if they occur before study completion:

1. Bradycardia: defined as a heart rate < 100 bpm for ≥ 20 seconds
2. Desaturation: defined as SpO₂ < 80% for ≥ 20 seconds
3. A sustained apnea event defined as lasting ≥ 20 seconds and coinciding with at least one of the following:
 - HR < 100 bpm
 - Desaturation (oxygen saturation < 80%)
4. Other AES of special interest have been adopted from England *et al.*'s adverse event tables for the Pediatric Trials Network (PTN) [23] (Appendix E).
5. Infections [21]

Definitions

Adverse Event

An adverse event (AE) is any symptom, sign, illness or experience that develops or worsens in severity during the course of the study. Intercurrent illnesses or injuries should be regarded as AEs. Abnormal results of diagnostic procedures are considered to be AEs if the abnormality:

- results in study withdrawal
- is associated with a serious AE
- is associated with clinical signs or symptoms
- leads to additional treatment or to further diagnostic tests
- is considered by the investigator to be of clinical significance

Serious Adverse Event

Serious AE (SAE) means any untoward medical occurrence at any dose: An event is “serious” if it involves considerable detriment or harm to one or more persons (who may or may not be participants), or required intervention to prevent one or more persons from experiencing considerable detriment or harm. SAEs include:

- Death
- Life-threatening experience – Disease or condition where the likelihood of death is high unless the course of the disease/condition is interrupted or diseases/conditions with potentially fatal outcomes where the endpoint of the clinical trial analysis is survival
- Inpatient hospitalization or prolongation of hospitalization
- Persistent or significant disability/incapacity
- Congenital anomaly/birth defect in participant's offspring

Title: Direct Peritoneal Resuscitation in Gastroscisis

PI: [name]

Sponsor: UAMS

- Any other important medical event that, based upon appropriate medical judgment, may jeopardize the participant and may require medical or surgical intervention to prevent one of the outcomes listed above. Examples include allergic bronchospasm requiring intensive treatment in an emergency room or at home, blood dyscrasias or convulsions that do not result in inpatient hospitalization, the development of drug dependency or drug abuse, suicidal ideation or attempts, or the unintentional revealing of some genetic information to insurers.

Related

An event is “related” if more likely than not it was caused by the research activity.

Unexpected

An event is “unexpected” when its specificity, nature, severity or incidence is not accurately reflected in the consent form, protocol, or investigator’s brochure previously reviewed and approved by the IRB. Examples include a lower rate of response to treatment or a side effect that is more severe than initially expected.

Study Period

All AEs will be recorded by the Investigator from the time of the start of study drug through the end of the designated follow-up period. All AEs will be recorded on the AE CRF. All relevant historical medical conditions that are known/diagnosed prior to the administration of study drug(s) are to be recorded.

Abnormal Laboratory Values Defined as AEs

An abnormal laboratory value is considered to be an AE if the laboratory abnormality is characterized by any of the following:

- Results in discontinuation from the study
- Requires treatment, modification of study drug dose, or any other therapeutic intervention
- Is judged by the Investigator to be of significant clinical impact/importance
- Grade 3 or Grade 4 lab abnormalities regardless of significance

If a laboratory abnormality is one component of a diagnosis or syndrome, then only the diagnosis or syndrome should be recorded as an AE. If the laboratory abnormality was not a part of a diagnosis or syndrome, then the abnormality should be recorded as the AE.

Monitoring, Recording and Reporting of AEs

All AEs occurring during the study period must be recorded. The clinical course of each event should be followed until resolution, stabilization, or until it has been determined that the study treatment or participation is not the cause. SAEs that are still ongoing at the end of the study period must be followed for up to 30 days to determine the final outcome. Any SAE that occurs after the study period and is considered to be possibly related to the study treatment or study participation should be recorded and reported immediately to the Sponsor.

All subjects will be monitored for AEs during the study. Assessments may include monitoring the subject's clinical symptoms; laboratory, pathological, radiological, or surgical findings; physical examination; or other appropriate tests and procedures.

Title: Direct Peritoneal Resuscitation in Gastroschisis

PI: [name]

Sponsor: UAMS

AE data collection and reporting, which are required as part of every study, are done to ensure the safety of subjects enrolled in the studies and those who will enroll in future protocols. AEs are to be reported in a routine fashion at scheduled times during the trial, such as with the annual continuing review to the IRB. Certain AEs must be reported in an expedited fashion to allow for timely monitoring of subject safety and care.

The reporting of these events depends on the characteristics of the event:

1. Seriousness (grading of event)
2. Relatedness to study treatment
3. Expectedness

Steps to Determine if the Event Requires Expedited Reporting:

1. Determine whether the adverse event is related to the investigational drug. Attribution categories are as follows:
 - Unrelated
 - Unlikely
 - Possible
 - Probable
 - Definite
2. Determine expectedness of event. Expected events are those previously identified resulting from administration of the agent. An adverse event is considered unexpected when the type or severity of the event is not listed in the package insert, protocol, or consent form.

Note: This includes all events that occur within 30 days of the last dose/use of protocol treatment. Any event occurring more than 30 days after the last dose that is possible, probably, or definitely attributable to the investigational drug must be reported according to the instructions above.

Expedited Reporting of AEs

Institutional Review Board Reporting

Only adverse events meeting the UPIRTSO (Unanticipated Problem Involving Risks to Subjects or Others) will need to be reported to the UAMS IRB within the required 10-day allotment of being notified of the event. UPIRTSO requires that an unanticipated problem meet the following qualifications: a) unanticipated or unexpected; b) related to the research; and c) involves new or increased risk to the subject(s). All other adverse events should be recorded and reported to the UAMS IRB at continuing review.

Sponsor Reporting

The Sponsor will be promptly notified of all SAEs that are related to the study intervention and unanticipated/unexpected. These SAEs will be reported to the Sponsor using the FDA MedWatch 3500A. All other SAEs will be reported to the Sponsor and FDA in the Annual Progress Report. The Sponsor will report events to FDA in accordance with 21 CFR 312.

Deaths that are related to research will be reported to the Sponsor immediately upon Investigator notification. A death due to a terminal condition of the research participant would be considered anticipated and not related to the research. THE SPONSOR WILL REPORT DEATHS TO FDA IN ACCORDANCE WITH 21 CFR 312.

Title: Direct Peritoneal Resuscitation in Gastroschisis

PI: [name]

Sponsor: UAMS

Monitoring

Clinical site monitoring will be conducted by the UAMS Office of Research Regulatory Affairs (ORRA) to ensure that the rights and well-being of trial participants are protected; that the reported trial data are accurate, complete, and verifiable; and that the conduct of the trial is in compliance with the currently approved protocol/amendment(s), ICH GCP, and applicable regulatory requirements.

Monitoring specialists from ORRA will conduct periodic on-site, comprehensive monitoring as determined by a protocol-specific monitoring plan, which will be provided by the ORRA Monitoring Unit.

Data Handling and Recordkeeping

The Principal Investigator will carefully monitor study procedures to protect the safety of research subjects, the quality of the data and the integrity of the study. All study subject material will be assigned a unique identifying code or number. The key to the code will be kept in a file on a password-protected computer in the principal investigator's locked office. The data files will be kept in a separate file on the password-protected computer in the principal investigator's locked office. The only individuals who will have access to the code and information that identifies the subject in this study will be limited to investigators on this study. All data will be de-identified after analysis is complete by destroying the code key. De-identified data will be maintained as per UAMS and ACRI policy (currently all data will be kept until the last subject is 21 years of age plus 2 years) and destroyed per institutional guidelines.

All ultrasound studies will be transferred and stored on a secure image server located in the PI's office. The studies will be labeled prior to performing the study with a coded identification number based on the patients MRN. A separate computer workstation connected to the image server will be used for image viewing and data analysis. The ultrasounds will be reviewed on this separate password-protected computer only viewed by study personnel. All data will be de-identified after analysis is complete by destroying the code key. De-identified data will be maintained as per UAMS policy (currently seven years after publication) and destroyed per institutional guidelines.

Data Analysis

Demographic variables will be assessed for differences between groups. Categorical variables will be examined using Fisher's Exact Test or Chi Square Test. Continuous data will be examined using Students' T-test. All tests will be two-sided assuming a significance level of 5%. The dependent variable will be tested to ensure the assumption of normality is met.

The primary outcome measure is time to full enteral feeds of 100 kcal/kg/day. Using a two-sample t-test, we estimated that a sample size of 20 in each of the two groups will yield at least 80% power to detect a 6-day difference in mean time to goal enteral feeds (100 kcal/kg/day) assuming a common standard deviation of 7 and a two-sided significance level of 5%.

The proposed data analyses and sample size calculations were conducted with the support of statisticians at ACRI using SAS® Software, Version 9.4[24].

Ethical Considerations

This study is to be conducted according to applicable government regulations and Institutional research policies and procedures.

Title: Direct Peritoneal Resuscitation in Gastroschisis

PI: [name]

Sponsor: UAMS

The parent(s)/LAR of each potential subject identified as meeting inclusion criteria for this study will be approached to discuss participation in this study by trained study personnel. The person obtaining consent will go over the informed consent comprehensively with the parent(s)/LAR. The risks and rationale of this study will be outlined and all questions will be answered. The volunteer natures of this project will be emphasized, including uninhibited withdrawal from the study at any time. No coercion or undue influence will be used in the consent process. A copy of the signed consent will be given to the subject's parent(s)/LAR, and the informed consent process will be documented in each subject's research record in a separate process note.

Ways of consenting parent(s)/LAR:

1. Mother or father (if mother and father are married)/LAR consented prenatally in OB/GYN clinic.
2. Mother or father (if mother and father are married)/LAR consented after birth via faxed consent to the OB unit and returned to PI. The faxed consent will then be witnessed by bedside nurse.
 - a. The person obtaining consent will fax a consent form to the OB unit and conduct the consent process conversation by phone once the mother or father/LAR has the form in hand.

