Hypotheses: We hypothesize that the DPR group will have a more benign hospital course as measured by time to full enteral feeds of 100 kcal/kg/day. We will also assess time to abdominal wall closure, time on TPN, length of hospital stay and intestinal motility post-closure using bedside ultrasounds. Secondly, we hypothesize that there will be no deleterious effects related to introducing the peritoneal dialysis solution into the silo.

Study Objectives

Primary Objectives:

1. To demonstrate that subjects treated with DPR will have a more benign hospital course as measured by time to full enteral feeds. The primary outcome measure will be time to full feeds of 100 kcal/kg/day. Secondary outcomes will include length of time until abdominal wall closure, time on TPN, time to intestinal motility, and total days in the hospital.
2. To demonstrate that the use of DPR in neonates with gastroschisis treated with staged silo closure will result in no significant changes in commonly measured clinical and laboratory safety parameters. This will be measured with more frequent clinical and laboratory assessments for the DPR group. Vital signs and strict intake and output will be monitored every 6 hours for 48 hours after the maximum dialysate infusion volume has been reached, then every 12 hours. Sodium, potassium, blood glucose and lactate levels will be monitored every 6 hours via heelstick, central/arterial line or venipuncture

Title: Direct Peritoneal Resuscitation in Gastroschisis

PI: [name]

Sponsor: UAMS

per NICU standard practice for 24 hours after the maximum dialysate infusion volume has been reached, then every 12 hours through Post-Closure Day 1.

Investigational Product

Dianeal PD-2 1.5% is a sterile, nonpyrogenic, hypertonic peritoneal dialysis solution containing dextrose, a monosaccharide, as the primary osmotic agent. Routine peritoneal dialysis in neonates and infants utilizes up to 40 mL/kg of dialysate per dwell. It will be administered via a 10 mm flat JP drain as a bolus infusion every 6 hours until the abdominal wall is closed (generally 3-5 days), but not to exceed 7 days maximum. The initial bolus infusion will be 10 mL/kg of Dianeal 1.5%. If tolerated, each subsequent infusion will be increased by 10 mL/kg of Dianeal 1.5% up to a goal infusion of 40 mL/kg (to a maximum volume of 100 mL) as tolerated.

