 - a. Maternal race/ethnicity, age, prenatal care, prenatal vaccination history* (as available) [21], any congenital anomalies that were diagnosed prenatally, maternal substance use history, infant or maternal toxicology screen results, maternal infection history* (including risk factors for infections (as available)) [21], maternal antenatal conditions, antenatal steroids, antenatal magnesium, prenatal ultrasound findings, obstetric antenatal conditions, multiplicity of births, delivery type, APGAR score, indications for C-section
4. Infection
 - a. Blood stream infection, total ventilation days, surgical site infection, and ventilator-associated pneumonia, drain or catheter-related infections
5. Surgery
 - a. Respiratory mode support with surgical time frame, lab values with surgical time frame, complications associated with surgical time frame, surgical procedures, complications
6. Interventions during this admission as recorded by the NICU for the Children's Hospital Network Database
7. Date of discharge from NICU
 - a. Discharge disposition
8. Patients discharge to home/foster care
9. Mortality
10. GI
 - a. Did this infant have functional or structural short gut syndrome at the time of discharge?
 - b. Classification of gastrochisis at time of silo placement - Imaging to be taken at time of initial evaluation.
 - i. Simple
 - ii. Complex: atresia, stenosis, perforation, volvulus
 - iii. Appearance

Title: Direct Peritoneal Resuscitation in Gastroscisis

PI: [name]

Sponsor: UAMS

1. Pristine
2. Matted bowel with peel
3. Staining of amniotic fluid
4. Staining of bowel serosa
- c. # of days of empiric antibiotics
- d. Type/Staging of closure of gastroscisis
- e. Complications associated with closure
- f. Additional closure techniques(s)
- g. Closure timing

11. Other complications

- a. Bacterial overgrowth, late ischemia, NEC, stricture, volvulus, malabsorption, transfer for bowel or liver transplant

12. Feeding and medications

- a. Medications and immunizations [21]
- b. Hyperalimentation
- c. Enteral feedings
 - i. Route of feeding at initiation
 - ii. Reached 100 kcal/kg/d
 - iii. Route of feeding when reached 100 kcal/kg/d
 1. Type of gavage/gastrostomy tube feeding
 - iv. Type of enteral nutrition when reached 100 kcal/kg/d
 - v. Change in feeding regimen
 1. Date change was made
 2. Why change was made

13. Ultrasound

- a. Cumulative motility
- b. Mean motility

14. Additional data

- a. Gastrostomy tube residuals: date, time, and cc

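### No rule says how death or transplant transfer enters hospital days and TPN days; a t-test on observed days would credit an early death to its own arm

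*Combined protocol and SAP*

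**What the plan says.** Under Study Objectives, the first primary objective takes time to full enteral feeds as its primary measure. The secondary outcomes listed with it include "time on TPN, time to intestinal motility, and total days in the hospital". Risks and Benefits names a shorter stay among the possible benefits, so fewer days is meant as the better result. The protocol gives no start or stop rule for either count of days.

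Data Analysis contains one sentence on method that could cover these outcomes: "Continuous data will be examined using Students' T-test". It stands in a paragraph that opens with demographic variables, and no sentence names an analysis for the secondary outcomes. The sample-size paragraph, also based on a two-sample t-test, deals with the primary outcome only.

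The events at issue are recorded. The list of data to be obtained has mortality, discharge disposition and, under other complications, "transfer for bowel or liver transplant". Nothing links these items to the comparison of hospital days or TPN days.

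**The concern.** Time to full feeds makes a death visible: the infant never reaches the endpoint, so the analyst has to decide what to do. Hospital days and TPN days do not. An infant who dies on day 5 has a recorded stay of 5 days, and nothing in the data looks missing. Put through the one test that the plan names, that value counts as a good result for the arm in which the infant died. A transplant transfer works in the same direction, because the count at this hospital stops while the illness goes on.

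These two outcomes would be read as support for the claim that DPR eases the hospital course. With 20 infants per arm, one or two such events can move a mean noticeably. With no rule in place, the choice between counting and excluding these infants could be made after the data are seen.

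**Working it through.** **The plan's own figure.** The plan states no mean difference, SD or power for hospital days or TPN days. Its one power statement ("a sample size of 20 in each of the two groups will yield at least 80% power") is for time to full feeds. With a 6-day difference and SD 7, an exact two-sided 5% t-test gives 75.2% and the normal approximation 77.4%. That shortfall is a separate matter and does not affect this point.

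**Inputs**
- Infants per arm: 20 (Data Analysis).
- Mean stay: 29 days, the historical average for simple gastroschisis (Background and Rationale). The same section also gives about 26 NICU days for uncomplicated cases.
- SD of stay: not given. Assumed 7 (the plan's value for a different outcome) or 14.
- Number and day of deaths: not given. Assumed 1 to 3 deaths in one arm, between day 3 and day 14.

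**Step 1: shift in the arm mean.** Suppose k infants die on day d, their observed days are entered, and each would otherwise have had the average stay. The arm mean then falls by k × (29 − d)/20.
- One death on day 5: (29 − 5)/20 = 1.2 days. Two: 2.4 days.
- One death on day 3: (29 − 3)/20 = 1.3 days. On day 14: (29 − 14)/20 = 0.75 days.
- With the 26-day figure, one death on day 5: (26 − 5)/20 = 1.05 days.

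**Step 2: against the noise.** With SD 7, the standard error of the difference is 7 × √(2/20) = 2.2 days; with SD 14 it is 4.4 days. One day-5 death therefore shifts the comparison by about half a standard error at SD 7 and about a quarter at SD 14.

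**Step 3: effect on the test.** A simulation used 40,000 replicates, 20 per arm, lognormal stays with mean 29 and no true treatment effect. In the DPR arm k infants died on day 7. The table gives the chance of a significant result (two-sided 5%) in favour of the arm with the deaths.

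| Deaths in one arm | Mean shift (days) | t-test on observed days, SD 7 | t-test, SD 14 | Rank test, death worst, SD 7 | Rank test, SD 14 |
|---|---|---|---|---|---|
| 0 | 0 | 2.6% | 2.3% | 2.5% | 2.4% |
| 1 | 1.1 | 4.6% | 4.0% | 0.9% | 1.1% |
| 2 | 2.2 | 8.5% | 5.9% | 0.2% | 0.3% |
| 3 | 3.3 | 15.5% | 9.2% | 0.0% | 0.1% |

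Under the t-test, each further death makes its own arm more likely to look better. Ranking deaths worst reverses this.

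**Step 4: transfers and TPN days.** The direction for a transfer follows from truncation: the observed count is below what it would have been. No size is given here, because the documents do not say when transfers happen or how long those infants would have stayed. TPN days share the direction for the same reason, but no mean TPN duration is stated, so that shift is not quantified.

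**The case against.** The strongest reply is that the plan does not do what is feared. A reader might infer that it counts deaths and transfers as short stays. No sentence says so: excluding, censoring or ranking these infants fits the text equally well, and even the use of the t-test here is inferred from a general sentence. That is correct, and it limits the point to a missing rule. It does not remove the point. The one named method, applied literally, gives a result in the wrong direction, and the most obvious alternative, exclusion, compares survivors only and hides the worst outcomes.

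Second, one death is a modest effect, deaths would be on record as serious adverse events, and the headline claim rests on time to full feeds. All of this stands and keeps the point below the level of a threat to the trial.

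Third, these infants may not all have observed values. Subject Withdrawal from Study ends data collection for withdrawn infants, and Safety Monitoring withdraws infants for certain complications. Individual Subject Discontinuation covers overlapping events but has assessments continue. Those sections need to be reconciled. Until they are, some of the sickest infants could be missing rather than short.

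Two further inferences are not supported. One is that transfers produce a large shift: a transfer on day 30 is not short against a 29-day mean ((30 − 29)/20 = +0.05 days), and any larger figure needs an assumed full stay for which the documents give no basis. The other is that readmission days are known and left out: re-admission is only a bare item under Demographics, with no dates or days.

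**Conclusion.** The concern holds as a gap in the analysis plan. Hospital days and TPN days have no rule for death or transplant transfer, and analysing observed days by t-test would reward an early death. The size is about 1.2 days of mean stay per day-5 death (0.75 to 1.3 days for deaths between day 14 and day 3). For one death on day 7, the chance of a falsely favourable significant result rises from about 2.5% to 4.0–4.6%; for three, to 9.2–15.5%. These figures assume that the deaths fall in one arm, that the affected infants would otherwise have had an average stay of 29 days, and that the SD is 7 or 14. The documents supply no event rate and no SD for these outcomes. With no deaths or transfers the problem does not arise. Because these are secondary outcomes and the remedy needs little, it is an improvement worth making before data are analysed, not a flaw in the primary comparison.

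**What to change.** Add to Data Analysis:

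1. Hospital days and TPN days are counted over the index admission, with start and stop defined.
2. The arms are compared by a rank test in which in-hospital death ranks worst, transfer for transplant next worst, and all other infants by their days. An acceptable alternative is time to discharge alive and time off TPN alive, with death and transfer as competing events.
3. Deaths and transfers are reported by arm beside each result.
4. Raw days among infants discharged alive are shown as description only.
5. The handling of withdrawn infants is stated, once the withdrawal and discontinuation sections agree.

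Readmission days should stay out of the definition unless their dates are confirmed to be collected.

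The cost is a few sentences in the combined protocol and analysis plan. Mortality, disposition, transplant transfer, NICU discharge date and parenteral nutrition are already on the data list; the team should confirm that hospital discharge dates and TPN start and stop dates are captured, which the outcomes need in any case. The downside is that the result is no longer a simple difference in mean days.
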